2.2. Background

BP is the most common autoimmune blistering skin disease, with an estimated annual incidence of 2.4 to 23 cases per million individuals. However, among people >80 years of age, the incidence ranges from 190 to 312 cases per million individuals. ^{6,7} The disease has a poor prognosis, which is directly attributable to the advanced age of the patient population and the comorbidities that can be present in this population. A recent meta-analysis calculated that the relative risk of death among patients with BP during a 1-year period is 2.93 times greater that of the general worldwide population (adjusted for age and sex). Studies examining the all-cause mortality among patients with BP beyond 1 year have reported higher death rates in the first year (20% to 27%) than in subsequent years (9% to 16%). The main causes of death were infections and cardiovascular disorders, which are attributable to both the older age of patients with BP and their use of corticosteroids and/or immunosuppressants.

In BP, the disruption of the dermal-epidermal junction by pathogenic autoantibodies results in large, tense bullae on the skin, progressing to epidermal erosion, crusting, and urticarial plaque formation. Without treatment, BP ultimately progresses to life-threatening complications, including (but not limited to) severe infections, functional impairment of vital organs, and iatrogenic conditions.

Corticosteroids (either topical or oral) are currently the first-line therapy for the treatment of patients with BP. For BP that is either localized or mild/moderate in severity, medical authorities recommend application of high-dose TCS of strong potency (such as clobetasol propionate at doses from 20 to 40 g/day). ^{9,10} Unfortunately, the use of TCS at such high doses results in a substantial systemic absorption and severe skin atrophy. ¹¹

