7.3. Lost to Follow-up

A participant will be considered lost to follow-up if they repeatedly fail to return for scheduled visits and cannot be contacted by the study site.

The following actions must be taken if a participant fails to return to the clinic for a required study visit:

- The site must attempt to contact the participant and reschedule the missed visit as soon as possible, counsel the participant on the importance of maintaining the assigned visit schedule, and ascertain whether the participant wishes to and/or should continue in the study.
- Before a participant is considered lost to follow-up, the investigator or designee must make every effort to regain contact with the participant (where possible, 3 phone calls, and if necessary, a certified letter to the participant's last known mailing address or local equivalent methods). These contact attempts should be documented in the participant's medical record.

- Should the participant continue to be unreachable, they will be considered to have withdrawn from the study.
- Site staff, or an independent third party, will attempt to collect the vital status of the participant within legal and ethical boundaries for all participants randomized, including those who did not get IMP. Public sources may be searched for vital status information. If vital status is determined as deceased, this will be documented and the participant will not be considered lost to follow-up. Sponsor staff will not be involved in any attempts to collect vital status information.

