8.4.1. Time Period and Frequency for Collecting Information on AEs, SAEs, and AESIs

All AEs, SAEs, and AESIs will be collected from the signing of the ICF until the last follow-up visit at the time points specified in the SoA (Table 1).

Medical occurrences that begin before the start of IMP but after obtaining informed consent will be recorded as non-treatment-emergent AEs; these will not be included in safety analyses.

All SAEs and AESIs will be recorded and reported to the sponsor or designee immediately; under no circumstance should the reporting time exceed 24 hours (Section 10.3.4). The investigator will submit any updated SAE data to the sponsor within 24 hours of it being available.

Investigators are not obligated to actively seek information on AEs or SAEs after conclusion of the study participation. However, if the investigator learns of any SAE, including a death, at any time after a participant has been discharged from the study, and they consider the event to be reasonably related to the IMP or study participation, the investigator must promptly notify the sponsor.

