5.1.2 Derivation rules

Treatment-emergent adverse events (TEAE) are defined as AEs starting within 60 days of an administration of IMP. Post-TEAEs are AEs starting after first administration of IMP that are not TEAEs.

Based on their start date/time, AEs will be allocated to the phase during which they started. Each AE will therefore be reported in only one phase. In case the AE start date/time is incomplete or missing and the AE could consequently be allocated to more than one phase, a worst-case allocation will be done as detailed below:

 Treatment phase vs. non-treatment phase: the AE will be allocated to the treatment phase unless the available parts of the AE start or stop date/time provide evidence for allocating to the non-treatment phase.

A death case is defined as an AE with outcome 'fatal'.

An AE for which the IMP was discontinued is defined as an AE with action taken 'drug withdrawn'.

AEs with missing treatment, prednisone or procedure relatedness will be considered as treatment-related, prednisone-related, or procedure-related respectively.

[figure not shown]
AEs with missing seriousness will be considered as serious AEs.

Adverse events of special interest will be defined using MedDRA system organ class 'Infections and infestations'.

Injection-related reactions (IRRs) will be defined as all AEs with MedDRA preferred terms that are listed in either:

- Hypersensitivity standardized MedDRA query (SMQ) (broad selection)
- Anaphylactic reaction (SMQ) (broad selection)
- Extravasation events (injections, infusions and implants) (SMQ) (broad selection), excluding implants

AND occurring within 48 hours of an administration, or within 2 days in case no AE start time is available. In case of (partially) missing AE start date, the AE will be considered as an IRR, unless the available parts of the AE start date provide evidence it did not occur within 48 hours of an injection.

Injection site reactions (ISR) will be defined as all AEs with a MedDRA high level term of "Injection site reaction", regardless of the time of AE onset relative to an administration.

AE onset and duration will be calculated as follows when start and stop dates are fully known:

- AE onset day (vs. first administration) =
 - AE start date ≥ date of first administration: AE start date date of first IMP administration + 1 day
 - AE start date < date of first administration: AE start date date of first IMP administration
- AE duration (days) =

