 - AE end date AE start date + 1 day
 - Study completion date or Study discontinuation date AE start date + 1 day (when the AE start date is fully known but the AE is not resolved at the end of the study)

In this case the duration will be presented as ">x days".

Event rates per 100 participant years of follow-up (PYFU) will be calculated as 100*number of events/PYFU, with:

- PYFU overall (in years) will be calculated as [the sum over all participants of the study duration calculated as (last phase end date – first IMP date + 1 day)]/365.25.
- PYFU for TEAEs (in years) will be calculated as above for PYFU overall with study duration cut off at 60 days after last IMP (i.e., last IMP date + 60 included) since AEs starting more than 60 days after last administration of IMP are not considered as TEAE.
- PYFU for post-TEAEs (in years) will be calculated as [the sum over all participants of all period durations during which an AE is considered to be post-treatment-emergent]/365.25.

Time to onset of first treatment-emergent adverse event (in days) will be calculated as date of the first treatment-emergent AE – date of first IMP administration + 1.

Participants without any TEAE will be censored at the date of the last IMP administration + 60 days or end date of the last analysis phase, whichever comes first. This info will be provided in the ADaM dataset (ADTTE); no tabulation is foreseen.

Similar time-to-event calculations will be done for:

- Time to onset of first serious TEAE
- Time to onset of fatal TEAE

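### The SAP recognises a death only as a fatal AE and makes no use of vital status, so some deaths after leaving the study, and deaths of undosed randomised participants, can go uncounted

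*SAP*

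**What the plan says.** **SAP.** Section 5.1.2 gives the only definition of death in the plan: "A death case is defined as an AE with outcome 'fatal". The SAP text does not mention vital status. Section 2.1.1 places safety analyses on the safety set, which is randomised participants who received at least one dose. Fatal TEAEs have a row in the AE overview table, and section 5.1.3 repeats that table for post-TEAEs and for all AEs in treatment plus follow-up. Table 14.3.1.17 shows fatal TEAEs by term, and Listing 16.2.7.3 shows fatal AEs. A time to fatal TEAE is derived in the same way as time to first TEAE, for which "no tabulation is foreseen". The output list in section 8 has no all-cause mortality table by randomised arm.

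Sections 4.1.2.1 and 4.1.2.2 make death before week 36 a main intercurrent event, handled as non-response. They do not say where the fact or date of death comes from.

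**Protocol.** Section 7.3 has site staff or a third party try to establish vital status "for all participants randomized, including those who did not get IMP", with public sources allowed. It continues: "If vital status is determined as deceased, this will be documented and the participant will not be considered lost to follow-up". It does not say that such a death becomes an AE. Under 8.4.1, "All AEs, SAEs, and AESIs will be collected from the signing of the ICF until the last follow-up visit". After participation ends there is no duty to search, and a death the investigator learns of must be notified if "they consider the event to be reasonably related to the IMP or study participation". Section 8.4.4 requires any death during the study to be reported as an SAE whatever its cause, and puts SAEs spontaneously reported within 30 days of the last visit into the safety database.

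**The concern.** The protocol sets up a route for finding deaths that the SAP's definition does not use. A death found by a vital-status search in someone who has left the study has no assured way into any SAP output. A death before dosing may well be reported as an SAE, but the participant is not in the population on which the tables and AE listings are run.

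Mortality matters in this disease. Protocol 2.2 cites first-year death rates of 20% to 27%, and protocol 9.3.3.3 describes the study population as having high mortality. Frail participants may leave shortly before they die, and leaving may differ between arms. A count that ends when a participant leaves could then distort the mortality comparison.

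There is also a link to efficacy. If the intercurrent event draws on the only death definition in the SAP, a death known only from vital status would not trigger the non-response rule.

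**Working it through.** The plan states no figure to reproduce. The check has two parts: which deaths reach an output, and how many might not.

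**1. Tracing deaths through the stated rules**

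- *Dosed, still in the study, on or off IMP.* An SAE under protocol 8.4.4 and a fatal AE under SAP 5.1.2. It is counted in the overall AE overview and listed, even if it falls outside the 60-day treatment-emergent window.
- *Withdrawn, but in the optional 7-week follow-up (protocol 7.2).* AE collection continues, so the death is counted.
- *Spontaneously reported within 30 days of the last visit.* It enters the safety database. The SAP's last analysis phase ends at trial termination (Table 1), and the SAP does not say whether these reports reach the tables.
- *Found by a vital-status search after the participant left.* It is documented, but no AE record is required by protocol 7.3. It can be missed.
- *Randomised, never dosed.* Covered by the vital-status attempt, but outside the safety set.

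**2. Size of the gap**

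Inputs: N = 120 (Part B) or 160 (Parts A and B); annual mortality q = 0.20 to 0.27 (protocol 2.2), taken as a constant hazard. The documents give no rate of leaving, so 5% to 15% leaving with 18 weeks remaining is assumed.

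Expected deaths by week 36 = N × [1 − (1 − q)^(36/52)]:

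- q = 0.20: 120 × (1 − 0.857) = 17.2
- q = 0.27: 120 × (1 − 0.804) = 23.5

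Expected deaths after leaving = N × (fraction leaving) × [1 − (1 − q)^(18/52)]:

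- Low: 120 × 0.05 × 0.0743 = 0.45
- High: 120 × 0.15 × 0.1032 = 1.86
- For N = 160: 0.59 to 2.48
- For N = 120 at q = 0.10: the bracket is 0.0358, giving 0.21 to 0.64

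As a second model, let leaving also have a constant hazard g, with h the death hazard and t = 36 × 7/365.25 years. Deaths after leaving are then N[1 − e^(−ht)] − N × h/(h + g) × [1 − e^(−(h+g)t)]. For N = 120 and 5% to 20% leaving by week 36, this gives 0.42 to 2.34.

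Both models treat every death after leaving as uncounted, so each is an upper bound under its assumptions.

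**3. Effect on efficacy**

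- *Primary analysis.* A participant with no disease status from week 32 to week 36 is already a non-responder (SAP 4.1.2.2), so an unrecorded death normally changes nothing. The exception is someone in CRoff at week 32 who leaves and dies before week 36: the last available status would count as a response.
- *Supplementary treatment-policy analysis.* A known death is non-response, while other missing week 36 data are multiply imputed. An unrecorded death is therefore handled like any other missing value and can become a response. If all 1.86 deaths fell in one arm of 60 and every one were imputed as a response, that arm's rate would rise by 1.86/60, or about 3 percentage points. The real effect would be smaller.

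**The case against.** The strongest reply is that the SAP already reports deaths adequately. Any-cause deaths in the study are SAEs. The overview runs beyond treatment-emergent events, and the fatal AE listing has no such restriction. Participants who stop IMP are encouraged to stay to week 36 (protocol 7.1.1), and those who withdraw are offered follow-up. A site that learns of a lost participant's death during the study may report it under protocol 8.4.4 in any case. Study discontinuation reasons are also tabulated (Table 14.1.1.7), although the documents supplied do not list the reasons. Mortality is not a listed endpoint, and the protocol plans descriptive safety summaries only.

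Most of this stands. It confines the gap to participants who leave entirely and to those never dosed. It does not close it, because protocol 7.3 does not require an AE record and the SAP names no other source of deaths.

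The objection is also right that vital status is an attempt subject to legal and ethical limits, with no row in the schedule of activities. After consent is withdrawn, protocol 7.2 confirms only the use of data already collected. Completeness cannot be assumed. The trial also requires a Karnofsky score of at least 60% and excludes significant serious disease, so mortality may be below the cited range.

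A reader might infer that deaths after withdrawal are necessarily missing, that deaths outside the treatment-emergent window are invisible, or that the primary result is compromised. The documents support none of these.

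**Conclusion.** The point holds as a limited gap in definition. Deaths learned of only through vital status after withdrawal or loss to follow-up can be left out, and deaths of randomised but undosed participants fall outside the safety set. In-study deaths of dosed participants are captured.

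The size is probably small: at most about 0.4 to 1.9 Part B deaths, under the assumed 5% to 15% leaving with 18 weeks remaining and 20% to 27% annual mortality at a constant hazard. At 10% mortality it is about 0.2 to 0.6. One or two deaths could still matter in a descriptive mortality comparison of arms of about 60, particularly if leaving differs by arm. The primary analysis is little affected. The supplementary treatment-policy analysis is open to an unrecorded death being imputed as a response. This is a worthwhile, low-cost improvement and does not threaten the trial's main conclusion.

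**What to change.** 1. In SAP 5.1.2, define death as a death from any recorded source: fatal AE, study-termination record or vital-status record, within consent and legal limits. State the cut-off date, and say whether deaths reported in the 30 days after the last visit are included.
2. Use that variable for the death intercurrent event in SAP 4.1.2 and for the death rule in the multiple imputation.
3. Add one table and one listing of all-cause deaths by randomised arm, in all randomised participants, through week 36. Show the number in each arm whose vital status is unknown.

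The cost is SAP wording, one derived variable and two outputs, from data the protocol already plans to seek. The downside is that vital status may be incomplete and some deaths will lack a cause or relatedness assessment. Any Kaplan-Meier summary should therefore be optional and descriptive.

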5.1.3 Presentation of results

Unless mentioned otherwise, tables will present TEAEs only.

The TEAE tables will be presented for the treatment and follow-up phase combined.

SGS	Statistical Analysis Plan	
ARGX-113-2009	Final and Interim Analysis	Final 4.0 of 04NOV2024

An overview table will show the number and percentage of participants with at least one event and the number of events and number of events per 100 participant years of follow-up for the following:

- TEAEs
- Treatment-related TEAEs
- Serious TEAEs
- Serious treatment-related TEAEs
- Serious prednisone-related TEAEs
- Grade ≥ 3 TEAEs
- Treatment-related Grade ≥ 3 TEAEs
- TEAEs related to prednisone (or equivalent OCS)
- TEAEs related to study procedures
- TEAEs for which the IMP was discontinued
- TEAEs for which the IMP was interrupted
- TEAEs of special interest
- Treatment-related TEAEs of special interest
- TE IRRs
- Serious TE IRRs
- TE ISR events
- Fatal TEAEs

This overview table will be repeated for:

- Post-TEAEs (AEs starting after first IMP administration but not considered treatment-emergent)
- All AEs during the treatment + follow-up phase (overall AEs)

A similar overview table will be created specifically for treatment-emergent ISR events and will show the number and percentage of participants with at least one event, the number of events and number of events per 100 participant years of follow-up for the following:

- Treatment-emergent ISRs (TEISRs)
- Treatment-related TEISRs
- Serious TEISRs
- Serious treatment related TEISRs
- Serious prednisone related TEISRs
- Grade ≥ 3 TEISRs
- Treatment-related Grade ≥ 3 TEISRs
- TEISRs related to prednisone (or equivalent OCS)
- TEISRs related to study procedures
- · TEISRs for which the IMP was discontinued

SGS	Statistical Analysis Plan	
ARGX-113-2009	Final and Interim Analysis	Final 4.0 of 04NOV2024

TEISRs for which the IMP was interrupted

[figure not shown]
A summary table of TEAEs by MedDRA system organ class and preferred term will show the number and percentage of participants with at least one event, the number of events and number of events per 100 participant years of follow-up.

This summary table will be repeated for:

- Post-TEAEs (AEs starting after first IMP administration but not considered treatment-emergent)
- All AEs during the treatment + follow-up phase (overall AEs)

Separate tables by MedDRA system organ class and preferred term will be prepared for the following, showing the number and percentage of participants with at least one event, the number of events and number of events per 100 participant years of follow-up:

- Treatment-related TEAEs
- Serious TEAEs
- Serious treatment-related TEAEs
- Serious prednisone-related TEAEs
- Grade ≥ 3 TEAEs
- Treatment-related Grade ≥ 3 TEAEs
- TEAEs related to prednisone
- TEAEs related to study procedures
- TEAEs for which the IMP was discontinued
- TEAEs of special interest
- Treatment-related TEAEs of special interest

- TE IRRs
- Serious TE IRRs
- TE ISR events
- Fatal TEAEs
- Common TEAEs (preferred terms occurring in at least 10% [5% for the
 analyses using pooled Part A and Part B data] of participants in either
 treatment group; the cut-off is applied after rounding to the nearest
 integer. System organ class will be presented if any preferred term
 within is selected.)

All AEs, including pre-treatment events will be listed. Furthermore, separate listings will be created for SAEs, fatal AEs, TEAEs leading to discontinuation of IMP and AESIs. A coding listing will indicate how individual terms have been coded to MedDRA system organ classes and preferred terms.

5.2 CLINICAL LABORATORY EVALUATION

5.2.1 Available data

Per protocol, the following safety laboratory parameters are expected:

[figure not shown]
- Biochemistry: sodium, potassium, calcium (total), HbA1c, creatinine, creatinine clearance, CRP, GGT, glucose, blood urea nitrogen (BUN), alanine aminotransferase (ALT/SGPT), aspartate aminotransferase (AST/SGOT), bilirubin (total and direct), low-density lipoprotein-cholesterol (LDL), high-density lipoprotein-cholesterol (HDL), total cholesterol, triglycerides, alkaline phosphatase (ALP), total protein, and albumin.
- Hematology: hemoglobin, hematocrit, mean corpuscular volume (MCV), mean corpuscular hemoglobin (MCH), % reticulocytes, red blood cell (RBC) count, platelet count, white blood cell (WBC) count with differential.
- Special laboratory tests: aPTT, INR.
- Urinalysis: specific gravity, pH, protein, glucose, ketones, blood, bilirubin, urobilinogen, nitrite, leukocyte esterase, and microscopic examination.

Normal ranges are available as provided by the laboratory.

5.2.2 Derivation rules

Toxicity grades will be computed according to the NCI CTCAE v5.0 grading list. The implementation of these toxicity grades for analysis is presented in appendix 9.4. Only the parameters described in appendix 9.4 will be computed, according to the declared limits for each grade.

The following abnormality categories will be defined:

- Low: value < lower limit of normal range
- Normal: lower limit of normal range ≤ value ≤ upper limit of normal range
- High: value > upper limit of normal range

Notes:

- Classification will be done by using non-imputed values and limits as
 reported in standardized units in the clinical database: a value <X where
 X equals the lower limit of normal range will be classified as low. A
 value X with normal range <X will be classified as high.
- For the worst-case analysis visits, an additional category low + high is defined in case there are both low and high post-baseline values.

The creatinine clearance or estimated glomerular filtration rate (eGFR) will be derived by the Chronic Kidney Disease Epidemiology Collaboration (CKD-EPI) formula if not already provided as such by the central lab:

```
eGFR (mL/min/1.73m²) = 141 * minimum(creatinine (mg/dL)/ K; 1)^{\alpha} * maximum(creatinine (mg/dL)/ K; 1)^{-1.209} * 0.993age (years) * [1.018 if female] * [1.159 if race = black] where K = 0.7 if female and K = 0.9 if male;
```

 $\alpha = -0.329$ if female and $\alpha = -0.411$ if male

Note: in case results in mg/dL are not available, results in μ mol/L will be used after conversion in mg/dL: 1 mg/dL = 88.4 μ mol/L

[figure not shown]
5.2.3 Presentation of results

The statistical analysis will present results in standardized units, except for eGFR that will be presented in mL/min/1.73m².

Continuous laboratory parameters will be summarized by means of descriptive statistics at each analysis visit. Actual values and changes from baseline will be shown in the same table. For albumin and low-density lipoprotein-cholesterol (LDL-C) also percent changes vs baseline will be shown.

Laboratory abnormalities for biochemistry and hematology parameters will be presented as a cross-tabulation (shift table) of the abnormality at each post-baseline analysis visit and at the worst-case analysis visit versus the baseline abnormality. This table will also show numbers of participants with treatment-emergent abnormalities (see Definition of terms). The denominator for the percentage is the total number of participants per treatment and per analysis visit in the safety analysis set. Tables for laboratory abnormalities will be restricted to biochemistry and hematology parameters.

Laboratory toxicity grades will be presented as a cross-tabulation (shift table) of the toxicity (NCI-CTCAE grades) at each post-baseline analysis visit and at the worst-case analysis visit versus the baseline toxicity. This table will also show numbers and cumulative numbers over decreasing toxicity grading of participants with treatment-emergent toxicities. The denominator for the percentage is the total number of

participants per treatment and per analysis visit in the safety analysis set. Parameters having toxicity grades defined in both directions (hypo and hyper) will be shown by direction.

All laboratory data will be listed, but only for participants with any post-baseline abnormality or toxicity or any overall interpretation of blood sample determined as clinically significant by the investigator, based on the sample for biochemistry or hematology parameters.

